## 10.9 Visits 23 (end of study)

**Visits 23** will be conducted in person at the clinical study site on Study Day 450 ± 5 days. This visit will include:

- A1c (blood sample sent to NGSP laboratory)
- Review of concomitant medications
- Height
- Weight
- Assessment of AEs since previous visit
- Return study devices (Omnipod Horizon™ System, CGM, BG and ketone meters)
- Complaints/device deficiencies such as occlusion alarms and system hazard alarms since last visit
- Device uploads for BG and ketone meter
- Data review of Automated Mode use by clinician

## 10.10 Unscheduled Visits (Phase 3)

Aside from scheduled visits, subjects may require an unscheduled visit either by telephone or in person at the clinical study site. All scheduled assessments will be performed according to Table 3: Schedule of Assessments for Phase 3. This visit will include, at a minimum:

- Review of concomitant medications

- Assessment of AEs since last visit
- Complaints/device deficiencies such as occlusion alarms and system hazard alarms since last visit
- Data review of Automated Mode use by clinician

Additional assessments may be warranted at the discretion of the investigator.

### **10.11 Early Withdrawal (Phase 3)**

Any subject may withdraw early from the study at any time for any reason. Upon withdrawal, assessments will be performed following Table 3: Schedule of Assessments for Phase 3. The investigator may also terminate a subject's participation in the study if it is in the best interest of the subject or if the Sponsor or local regulatory agency (e.g., FDA) terminates the study.

The Early Withdrawal visit will include:

- A1C (blood sample sent to NGSP laboratory)
- Review of concomitant medications
- Height
- Weight
- Assessment of AEs since last visit
- Return study devices (Omnipod Horizon™ System, CGM, BG and ketone meters)
- Complaints/device deficiencies such as occlusion alarms and system hazard alarms since last visit
- Device uploads for BG and ketone meter
- Data review by clinician

The reason for withdrawal will be recorded, and their participation in the study will end.

In the event of a subject's death during the study, the subject's participation will be considered terminated and the date of death will be used as the date of study exit.

### **10.12 Lost to Follow-up**

Every effort will be made to contact a subject in the event of a missed scheduled visit. A subject will be considered lost to follow-up if they are inaccessible by two or more different methods of contact and fail to show up for two scheduled visits. The site will document each attempt made to contact the subject and specify the reason for early withdrawal as lost to follow-up.

## **11 SPONSOR REPRESENTATIVES**

One or more representatives of the Sponsor may be present at the hybrid closed-loop clinical study site visits under supervision of the investigator.

## 12 SAFETY

### 12.1 Types of Known Risks and Benefits

There are known risks and benefits. Most of the risks are not unique to the study and are typical for patients using insulin pumps, CGM, and BG meters.

The known risks are as follows:

- Hypoglycemia and/or hyperglycemia as a result of change in diet, activity, diabetes management or insulin regimen during the study.
- Hypoglycemia and/or hyperglycemia as a result of over or under delivery of insulin due to a device defect, failure or malfunction of any of the system components.
- Hypoglycemia, hyperglycemia, diabetic ketoacidosis, seizure, coma or death related to insulin administration, pump use or misuse, or Horizon™ System use or misuse.
- Use of the Pod (Omnipod® tubeless, insulin delivery pump) - Because the Pod uses only rapid-acting insulin, users are at increased risk for developing hyperglycemia if insulin delivery is interrupted. If it is untreated, prolonged hyperglycemia can quickly lead to diabetic ketoacidosis (DKA). DKA can cause symptoms such as breathing difficulties, shock, coma, or death. Further, occlusions can interrupt insulin delivery and lead to hyperglycemia or DKA. Other potential risks associated with using the Pod are:
  - Anaphylaxis (allergic shock)
  - Bruising at the Pod site
  - Bleeding at the Pod site
  - Erythema (redness at the Pod site)
  - Excoriation (raw skin at Pod site)
  - Pruritus (itching)
  - Induration (hardening of the skin at the Pod site)
  - Infection (can include heat, redness, swelling, pain, and drainage)
  - Inflammation (redness, swelling)
  - Skin reaction to adhesive at the Pod site
  - Papule (small, solid raised area on the skin similar to a pimple)
  - Pain or discomfort
  - Ulceration (skin sores)
  - Vesicles (blisters)
- Use of the CGM - risk of bruising, infection, pain and/or bleeding at the site of insertion, and skin site reaction to adhesive

- On rare occasions, the CGM sensor may break and leave a small portion of the sensor under the skin that may cause redness, swelling, or pain at the insertion site, and may require surgical removal.
- Blood sampling with fingerstick - minor discomfort and risk of infection at site of fingerstick

There are several potential benefits from this study. The Omnipod Horizon™ System is designed to provide automated glucose control. The system is expected to reduce hypoglycemia without incurring an unacceptable increase in hyperglycemia and mean glucose. The system is also expected to reduce the extent and magnitude of hyperglycemia associated with meals. The Omnipod Horizon™ System uses a control-to-target strategy that attempts to achieve and maintain a set target glucose level.

## 12.2 Hypoglycemia/Hyperglycemia

Subjects will be asked to treat per their usual routine if they suspect either hypoglycemia or hyperglycemia, either by confirmation of hypoglycemia with a fingerstick BG, symptoms, or perceived risk.

Subjects will be encouraged to manage their hyperglycemia per their usual routine. This includes checking for ketones using the study-approved ketone meter and administering a correction bolus if needed.

In the event of unexplained hyperglycemia, where the CGM is  $>300\text{mg/dL}$  for 1h or  $>250\text{ mg/dL}$  for 2h, blood glucose (measured with BG meter) and ketones should be checked. If BG is  $\geq300\text{ mg/dL}$  and ketones are  $>1.0\text{ mmol/L}$ , an occlusion or dislodged cannula should be suspected. The Pod should be removed, and the subject will be instructed to replace the Pod. Subjects should contact the clinical site for further instructions to determine whether an additional injection of insulin is required. This prolonged hyperglycemic event, defined as meter BG  $\geq300\text{ mg/dL}$  and ketones  $>1.0\text{ mmol/L}$ , will be recorded as an adverse event and cause may be attributed to suspected occlusion if the cannula is in situ or dislodged cannula if it has been pulled out. Pods will be requested to be returned to Insulet for analysis. An Adverse Event form will be completed per the Reportable Adverse Events section below.

## 12.3 Adverse Events

### 12.3.1 Definitions

**Adverse Event (AE):** is defined as any untoward medical occurrence, unintended disease or injury, or any untoward clinical signs (including an abnormal laboratory finding) in subjects, users or other persons, whether or not related to the investigational medical device.

NOTE 1: This includes events related to the investigational medical device or the comparator.

NOTE 2: This definition includes events related to the procedures involved (any procedure in the clinical investigation plan).

**Serious Adverse Event (SAE):** Any untoward medical occurrence that:

- Led to death
- Led to serious deterioration in the health of the subject, that either resulted in:
  - a life-threatening illness or injury, or
  - a permanent impairment of a body structure or a body function, or
  - in-patient or prolonged hospitalization, or
  - medical or surgical intervention to prevent life-threatening illness or injury or permanent impairment to a body structure or a body function.
- Led to fetal distress, fetal death, or a congenital abnormality or birth defect.

NOTE: Planned hospitalization for a pre-existing condition, or a procedure required by the clinical investigational plan, without serious deterioration in health, is not considered a serious adverse event.

**Unanticipated Adverse Device Effect (UADE):** Any serious adverse effect on health or safety or any life-threatening problem or death caused by, or associated with, a device, if that effect, problem, or death was not previously identified in nature, severity, or degree of incidence in the investigational plan or application (including a supplementary plan or application), or any other unanticipated serious problem associated with a device that relates to the rights, safety, or welfare of participants.

**Adverse Device Effect (ADE):** An adverse device effect (ADE) is an adverse event related to the use of an investigational medical device.

NOTE 1: This definition includes any adverse event resulting from insufficient or inadequate instructions for use, deployment, implantation, installation, or operation, or any malfunction of the investigational medical device.

NOTE 2: This definition includes any event resulting from user error or from intentional misuse of the investigational medical device.

An event that occurs solely due to participant (i.e., user) error in which the device functions properly generally will not be considered an ADE unless it is determined that the instructions on the screen of the device or user manual (or similar training materials) may have contributed to the event (note: the event may still meet criteria for reporting as an adverse event).

**Serious Adverse Device Effect (SADE):** A serious adverse device effect is defined as an adverse device effect that has resulted in any of the consequences characteristic of a serious adverse event.

**Device Deficiency (DD):** A device deficiency is defined as a device related complaint or malfunction or any inadequacy of a device with respect to its identity, quality, durability, reliability, safety or performance and includes misuse or use errors and inadequate labeling. A device deficiency is something that happens to a device or is related to device performance, whereas an adverse event happens to a participant. A device deficiency may occur independently from an AE, or

along with an AE. An AE may occur without a device deficiency or there may be an AE related to a device deficiency.

Note: for reporting purposes, sites will not be asked to distinguish between device complaints and malfunctions.

For any event where there is suspicion that the study device is involved, the Sponsor will request that the investigator return the device for evaluation.

All device complaints or malfunctions involving any investigational component of the Omnipod Horizon™ System used in the study will be reported to the Sponsor within 5 business days of knowledge of the deficiency and documented on an appropriate eCRF. All study product associated with a reported device deficiency (PDM, Pod, and CGM) should be retained at the clinical site and returned to the Sponsor or CGM manufacturer for investigation and analysis.

### **12.3.2 Reportable Adverse Events**

Adverse events will be assessed on an ongoing basis throughout the study. Adverse event reporting will begin at the start time of the standard therapy phase (i.e., insertion of the CGM sensor) and continue through the hybrid closed-loop phase 2 and 3 until the subject's participation has ended. All adverse events must be followed until resolution, or until the AE has stabilized, or until the study has been completed.

Pre-existing medical conditions or symptoms observed prior to the start time of the standard therapy phase will not be recorded as an AE and should be collected in the subject's medical history. In the event there is a change (i.e., worsening) in the pre-existing medical condition or symptoms after enrollment meeting the criteria of a reportable adverse event, then an AE must be reported.

For this protocol, a reportable adverse event includes any untoward medical occurrence that meets one of the following criteria:

1. An SAE
2. An ADE unless excluded from reporting in Hypoglycemic Events and Hyperglycemic/Ketotic Events sections below
3. An AE occurring in association with a study procedure
4. An AE not related to a study device issue which leads to temporary or permanent discontinuation of the study device
5. An AE that affects the participant's ability to complete any study procedures
6. An AE for which a visit is made to a hospital emergency department
7. Hypoglycemic Events as defined below
8. Hyperglycemia/Ketotic Events as defined

Skin reactions from sensor or pod placement are only reportable if severe and/or required treatment.

For the purpose of this protocol, mild symptoms of hypoglycemia and hyperglycemia (i.e., clinically non-significant) or blood glucose values out of the normal range (whether or not they resulted in delayed meals or correction boluses) will not be reported as AEs unless determined to meet the reportable criteria in the Hypoglycemic Events and Hyperglycemic/Ketotic Events sections below.

All reportable AEs—whether volunteered by the participant, discovered by study personnel during questioning, or detected through physical examination, laboratory test, or other means—will be reported on an AE eCRF.

### **12.3.3 Hypoglycemic Events**

Hypoglycemia is only reportable as an adverse event when one of the following criteria is met:

- Severe Hypoglycemia: The event required assistance of another person due to altered consciousness, and required another person to actively administer carbohydrate, glucagon, or other resuscitative actions. This means that the participant was impaired cognitively to the point that he/she was unable to treat himself/herself, was unable to verbalize his/her needs, was incoherent, disoriented, and/or combative, or experienced seizure or loss of consciousness. These episodes may be associated with sufficient neuroglycopenia to induce seizure or loss of consciousness. If plasma glucose measurements are not available during such an event, neurological recovery attributable to the restoration of plasma glucose to normal is considered sufficient evidence that the event was induced by a low plasma glucose concentration.
- Hypoglycemia resulting in an SAE that may not otherwise meet the definition of Severe Hypoglycemia defined above.

When a hypoglycemic event meets the above reporting requirements, an Adverse Event Form should be completed. A severe hypoglycemia event should be considered a serious adverse event and follow the SAE reporting requirements.

### **12.3.4 Hyperglycemic/Ketotic Events**

Hyperglycemia is only reportable as an adverse event when any of the following criteria is met:

- The event involved DKA, as defined by the Diabetes Control and Complications Trial (DCCT) and described below
- Evaluation or treatment was obtained at a health care provider facility for an acute event involving hyperglycemia or ketosis, or the participant contacted the site and received guidance on how to manage the hyperglycemia/ketosis
- Prolonged hyperglycemia: defined as meter BG  $\geq 300$  mg/dL and ketones  $> 1.0$  mmol/L
- Hyperglycemia resulting in an SAE that may not otherwise meet the above criteria

Hyperglycemic events are classified as DKA if all of the following are present:

- Symptoms such as polyuria, polydipsia, nausea, or vomiting;

- Serum ketones >1.5 mmol/L or large/moderate urine ketones;
- Either arterial blood pH <7.30 or venous pH <7.24 or serum bicarbonate <15; and
- Treatment provided in a health care facility

When a hyperglycemia/ketotic event meets the above reporting requirements, Adverse Event Form should be completed.

Events meeting DKA criteria should be considered a serious adverse event and follow the SAE reporting requirements. Hyperglycemia events not meeting criteria for DKA generally will not be considered as serious adverse events unless one of the SAE criteria above is met.

#### **12.3.5 Relationship of Adverse Event to Investigational Device**

The investigator will be responsible for making a determination on the causal relationship of the AE. Specifically, the investigator will report whether the AE was related to study procedures and/or related to the investigational device.

To ensure consistency of adverse event causality assessments, investigators should apply the following general guideline when determining whether an adverse event is related.

The causal relationship to the study procedures and the investigational device for each adverse event will be rated as follows:

- Unrelated: The event is not related to the procedures or the investigational device.
- Possibly Related: The temporal sequence is such that the relationship is not unlikely or there is no contradicting evidence that can reasonably explain the subject's condition. There is a possibility of any relation between the event and the procedures or the investigational device.
- Related: The temporal sequence is relevant or the event abates upon completion of the procedure/ investigational device, or the event cannot be reasonably explained by the subject's condition or comorbidities. The event is related or most likely associated with the procedures or the investigational device.

#### **12.3.6 Severity (Intensity) of Adverse Events**

The severity (intensity) of an adverse event will be rated on a three-point scale: (1) mild, (2) moderate, or (3) severe. A severity assessment is a clinical determination of the intensity of an event. Thus, a severe adverse event is not necessarily serious. For example, itching for several days may be rated as severe, but may not be clinically serious.

- **MILD**: Usually transient, requires no special treatment, and does not interfere with the participant's daily activities.
- **MODERATE**: Usually causes a low level of inconvenience, discomfort or concern to the participant and may interfere with daily activities but is

usually ameliorated by simple therapeutic measures and participant is able to continue in study.

- SEVERE: Interrupts a participant's usual daily activities, causes severe discomfort, may cause discontinuation of study device, and generally requires systemic drug therapy or other treatment.

#### 12.3.7 Outcome of Adverse Events

The outcome of each reportable adverse event will be classified by the investigator as follows:

- RECOVERED/RESOLVED - The participant recovered from the AE/SAE without sequelae. Record the AE/SAE stop date.
- RECOVERED/RESOLVED WITH SEQUELAE - The event persisted and had stabilized without further anticipated change in the event status. Record the AE/SAE stop date.
- FATAL - A fatal outcome is defined as the SAE that resulted in death. Only the event that was the cause of death should be reported as fatal. AEs/SAEs that were ongoing at the time of death; however, were not the cause of death, will be recorded as "resolved" at the time of death.
- NOT RECOVERED/NOT RESOLVED (ONGOING) - An ongoing AE/SAE is defined as the event was ongoing with an undetermined outcome.
  - An ongoing outcome will require follow-up by the site in order to determine the final outcome of the AE/SAE or until participant completes the study.
  - The outcome of an ongoing event at the time of death that was not the cause of death, will be updated and recorded as "resolved" with the date of death recorded as the stop date.
- UNKNOWN - An unknown outcome is defined as an inability to access the participant or the participant's records to determine the outcome (for example, a participant that was lost to follow-up).

If any UADEs are ongoing when a participant completes the study (or withdraws), the subject will continue to be followed until the event resolves or has no prospect of improvement or change, even after the participant has completed all applicable study visits/contacts, unless that subject has withdrawn their consent. For all other reportable adverse events, data collection will end at the time the participant completes the study. Note: Participants should continue to receive appropriate medical care for an adverse event after their participation in the study ends.

#### 12.4 Reportable Device Issues

Device complaints and device malfunctions will be reported except in the following circumstances. These occurrences are expected and will not be reported on a Device Deficiency Form:

- CGM sensor or Pod lasting fewer days than expected per manufacturer
- CGM tape or Pod adherence issues
- Battery lifespan deficiency due to inadequate charging or extensive wireless communication

- Intermittent device component disconnections/communication failures not requiring system replacement or workaround/resolution not specified in user guide/manual.
- Device issues clearly addressed in the user guide manual that do not require additional troubleshooting

## 12.5 Timing of Event Reporting

SAEs possibly related or related to a study device or study procedures and UADEs must be reported to the Sponsor/CRO within 2 business days of the site becoming aware of the event. This can occur via phone or email, or by completion of the AE eCRF. If the form is not initially completed, it should be completed as soon as possible after there is sufficient information to evaluate the event. All other reportable AEs should be submitted by completion of the AE eCRF within 5 business days of the site becoming aware of the event.

Each principal investigator is responsible for reporting adverse events required by this protocol and abiding by any other reporting requirements specific to his/her Institutional Review Board or Ethics Committee.

Upon receipt of a UADE report, the Sponsor will investigate the UADE and if indicated, report the results of the investigation to all participating investigators, overseeing IRBs, and the FDA within 10 business days of the Sponsor becoming aware of the UADE per 21CFR 812.46(b). Copies of the associated reports and correspondence with the investigators, regulatory authorities, and Sponsor must be retained with study records.

The Medical Monitor must notify the DSMB of any UADEs and determine if the UADE presents an unreasonable risk to participants. If so, the Sponsor must ensure that all investigations, or parts of investigations presenting that risk, are terminated as soon as possible but no later than 5 working days after the Medical Monitor makes this determination and no later than 15 working days after first notice of the UADE.

Device deficiencies will be handled by the Sponsor or designee as described below. In the case of a Dexcom CGM transmitter or sensor device malfunction, information will be forwarded to Dexcom by the site personnel, to be handled by Dexcom's complaint management system.

If the subject is hospitalized because of or during the course of an SAE, then a copy of the hospital discharge summary must be requested for inclusion with the SAE documentation. In case of death, the investigator must make every effort to obtain a copy of the death certificate to submit to the Sponsor. When submitting copies of documentation, all subject identifying information must be redacted and only the unique subject number will be used to label the forms for identification purposes.

For any event where there is suspicion that the study device is involved, the investigator will return the device for evaluation when possible.

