## 12.6 Safety Oversight

The study Medical Monitor will review all adverse events and adverse device events that are reported during the study. SAEs will typically be reviewed within 24-hours of reporting. Other AEs will typically be reviewed approximately weekly.

A Data and Safety Monitoring Board (DSMB) will be informed of all cases of severe hypoglycemia and diabetic ketoacidosis irrespective of device relationship, all UADEs during the study and will review compiled safety data at periodic intervals. The DSMB also will be informed of any SADEs and ADEs not meeting criteria for a UADE if the Medical Monitor requests the DSMB review. The DSMB can request modifications to the study protocol or suspension or outright stoppage of the study if deemed necessary based on the totality of safety data available. Details regarding DSMB review will be documented in a separate DSMB Charter.

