## 12.7 Stopping Criteria

### 12.7.1 Participant Discontinuation of Study Participation

In the case of a UADE, the Medical Monitor will determine if the use of the study device will be suspended while the problem is diagnosed. The use of the study device may continue if the Medical Monitor believes the event is explainable, unlikely to reoccur and that it is safe for the subject to continue using the device. Alternately, the Medical Monitor may request the study subject, or all study subjects, to stop using the study device or to only use in Manual Mode. Should all study subjects be required to stop using the study device or to only use in Manual Mode due an UADE, use of the study device or Automated Mode will not be restarted until approval is received from the IRB, DSMB and FDA.

Use of the study device by a participant will be discontinued if any of the following occur:

- The investigator believes it is unsafe for the participant to continue on the intervention. This could be due to the development of a new medical condition or worsening of an existing condition; or participant behavior contrary to the indications for use of the device that imposes on the participant's safety.
- The participant requests that the treatment be stopped
- Participant pregnancy
- Two distinct episodes of DKA as defined above
- Two distinct severe hypoglycemia events as defined above
- One episode of DKA and one severe hypoglycemia event as defined above

An additional requirement for continued study device use following a single DKA or severe hypoglycemia event will be that (1) the site investigator believes that the event is explainable, unlikely to recur, and that it is safe for the participant to continue to use the system and (2) the Medical Monitor concurs. If the Medical Monitor determines that the occurrence of the event indicates that it is not safe for the participant to continue to use the system, use will be discontinued, and the subject will be withdrawn from the study.

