## 12.9 Medical Monitor

An independent Medical Monitor will be responsible for individual and timely review of adverse events as defined below. The Medical Monitor will be a physician with relevant therapeutic and medical expertise that is not participating as an Investigator in the study and does not have a financial, scientific, or other conflict of interest with the clinical study.

Specific responsibilities of the Medical Monitor include:

- Review of all adverse events reported during the study
- Review all serious study procedure-related and/or investigational device-related adverse events to determine if the adverse event warrants consideration as a UADE and facilitate the reporting of UADEs if applicable
- Adjudicate the following(a) all SAEs; (b) any events of Diabetic Ketoacidosis or Severe Hypoglycemia; (c) all AEs reported by the site as related or possibly related to the investigational device; and/or (d) any additional events as requested by the Sponsor.
- The specified events will be adjudicated to determine:
  - event relatedness to the study procedures and/or the investigational device
  - event categorization and assess seriousness and severity
  - whether an adverse event is anticipated or unanticipated

The adjudication decision of the Medical Monitor will be used for the final classification of events, including relatedness to the study procedures and/or the

investigational device, for the determination of safety endpoints and for all regulatory reports, product labeling, and publications or presentations.

The Medical Monitor's roles and responsibilities are described in the Safety Management Plan (SMP).

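### Section 12.5 lets a severe hypoglycemia or DKA event that the site rates unrelated be reported at 5 rather than 2 business days, although the oversight rules for these two events ignore relatedness

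*Protocol*

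**What the plan says.** Protocol section 12.5 sets two reporting limits, both counted from the site becoming aware of the event.

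- **Fast limit:** "SAEs possibly related or related to a study device or study procedures and UADEs must be reported to the Sponsor/CRO within 2 business days". First notice may be by phone, email or eCRF.
- **Slower limit:** "All other reportable AEs should be submitted by completion of the AE eCRF within 5 business days". Only the eCRF is named here, and the verb is weaker (should, not must).

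The rating that separates the two comes from the site. Under 12.3.5, "the investigator will report whether the AE was related to study procedures and/or related to the investigational device", on a scale of unrelated, possibly related or related.

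Five other sections deal with severe hypoglycemia and DKA:

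- 12.3.3: "A severe hypoglycemia event should be considered a serious adverse event and follow the SAE reporting requirements".
- 12.3.4: "Events meeting DKA criteria should be considered a serious adverse event and follow the SAE reporting requirements".
- 12.6: the DSMB "will be informed of all cases of severe hypoglycemia and diabetic ketoacidosis irrespective of device relationship". The same section says that the Medical Monitor typically reviews SAEs within 24 hours, counted from reporting.
- 12.7.1 begins "An additional requirement for continued study device use following a single DKA or severe hypoglycemia event will be that" and then names two conditions: the investigator judges that it is safe to go on, and the Medical Monitor concurs. Relatedness plays no part.
- 12.9: the Medical Monitor adjudicates all SAEs and all events of these two kinds, including "event relatedness to the study procedures and/or the investigational device", and that decision gives the final classification. SAP section 5.1 repeats this.

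**The concern.** For these two events, the rating that sets the reporting limit is provisional. It belongs to the site and can be overturned by the Medical Monitor, who cannot begin until the report arrives. A site that is wrong in calling an event unrelated thus also gives itself more time before anyone can correct the call.

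Severe hypoglycemia and DKA are the two primary safety endpoints (Protocol 6.1.1), the basis on which the study is declared successful (SAP 2.5), and the events whose rates inform the stopping criteria (Protocol 12.7.2). The individual discontinuation rules in 12.7.1 also count them without regard to cause. What is at stake is the speed of oversight: how soon the Medical Monitor can give or withhold concurrence, and how soon a device pattern could be noticed.

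**Working it through.** The plan states no figure to reproduce. The check has two parts.

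**1. Which limit applies to an event rated unrelated**

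1. Section 12.3.2 makes every SAE reportable, whatever its cause.
2. Sections 12.3.3 and 12.3.4 make every severe hypoglycemia and DKA event an SAE and refer to the SAE reporting requirements, but give no time limit of their own.
3. The time limits stand in 12.5. Section 15.8 only points back to the timeline in the protocol.
4. Section 12.5 has no limit for SAEs as such. It has one for related or possibly related SAEs and UADEs, and one for everything else that is reportable.
5. An event of either kind that the site rates unrelated, and that is not a UADE, is therefore in the second group, at 5 business days. The cross-references in step 2 do not move it.

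**2. What the difference amounts to**

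Inputs: 2 and 5 business days (12.5) and a typical review within 24 hours of reporting (12.6), taken as 1 calendar day. Assumptions: a Monday to Friday working week, no holidays, the day of awareness counted as day 0, and weekend awareness counted from the preceding Friday.

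Days to Medical Monitor review = calendar days to the reporting limit + 1.

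| Site becomes aware | 2 business days, in calendar days | 5 business days, in calendar days | Difference | Reviewed by about day |
|---|---|---|---|---|
| Mon, Tue, Wed | 2 | 7 | 7 − 2 = 5 | 3 v 8 |
| Thu, Fri | 4 | 7 | 7 − 4 = 3 | 5 v 8 |
| Sat | 3 | 6 | 6 − 3 = 3 | 4 v 7 |
| Sun | 2 | 5 | 5 − 2 = 3 | 3 v 6 |

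The later limit therefore adds 3 to 5 calendar days. Because the 24-hour review runs from reporting, it adds the same day to both columns and does not narrow the gap. If weekend awareness were instead counted from the following Monday, the limits would fall on Wednesday and on the Monday after. That is a difference of 5 days, still within the range.

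**The case against.** **The cross-reference may already settle it.** The only limit in 12.5 worded for SAEs is the 2-day one, so sending severe hypoglycemia and DKA to the SAE requirements may have been meant to place them there. That is a fair guess at intent. But 12.5 makes that limit conditional on relatedness, so the text does not say it. If this was the intent, the change merely records it.

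**Few events may be affected.** *Possibly Related* is a low threshold: any possibility of a relation is enough, and a relation to study procedures counts too, so an event attributed to an exercise challenge can already qualify. This stands. On the other side, 12.3.1 says that an event due solely to user error will generally not be treated as a device effect, so an *Unrelated* rating is conceivable. The documents give no frequency, and a reader should not infer that such ratings would be common.

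**Extra days on the device without concurrence.** A reader might infer that 12.5 lets a participant use the device for up to 5 further days before the Medical Monitor has agreed. The documents do not support that. Section 12.7.1 makes concurrence a requirement for continued use, and a reporting maximum in 12.5 does not waive it. What is true is that 12.7.1 gives no deadline and does not say what holds in the interval, and that no rule obliges the site to call sooner. Even at 2 business days an interval of about 3 to 5 calendar days remains.

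**Other documents may be tighter.** The Safety Management Plan and the DSMB Charter are not available here and may set shorter times. That limits what can be said about practice, though not about the wording of 12.5.

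**Conclusion.** The point holds for severe hypoglycemia and DKA. As written, 12.5 allows an event of either kind that the site rates unrelated to be reported at 5 business days, which is out of step with 12.3.3, 12.3.4, 12.6, 12.7.1 and 12.9. The effect is a possible delay of 3 to 5 calendar days in Medical Monitor review. This assumes no holidays, reporting at the limit in both cases, and the typical review time.

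Two wider conclusions do not follow. The primary safety endpoints are not biased: all these events remain reportable and are adjudicated, so counts and the success criterion are unaffected. Nor is there a contradiction for other SAEs: the concurrence rule and the DSMB notice irrespective of relationship name only these two events, and no section conflicts with tiering the remaining SAEs by relatedness.

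This is an inexpensive improvement to safety oversight. It is not a threat to the trial's conclusions.

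**What to change.** In 12.5, add to the 2-business-day category: *and all severe hypoglycemia and DKA events regardless of relationship*. Make clear that phone or email first notice is allowed for them, as it already is for that category, and align the Safety Management Plan.

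Reconcile 12.5 with 12.7.1 on the interval between the event and the Medical Monitor's concurrence, so that a site can tell from the protocol what applies meanwhile. What that rule should be is a clinical decision for the sponsor and the Medical Monitor, and none is proposed here.

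Extending the 2-day limit to all other unrelated SAEs is optional; no section requires it.

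The cost is one clause, a matching edit to the Safety Management Plan, and slightly faster first notice from sites for a few events. The 5-business-day limit for other reportable events can stay.
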